2. STATISTICAL PLAN

The study will implement the intention-to-treat (ITT) principle, or, "analyze as randomized", which is recognized as an important protection against bias, namely balancing both known and unknown factors and eliminating selection bias. We will first compare the study subjects demographic and clinical factors to ensure the comparability between two treatment groups. For categorical variables, counts and percentages will be calculated and chi-square test or Fisher's exact test will be performed. For continuous variables, Shapiro-Wilk normality test will be performed, and either t-test or Wilcoxon rank test will be performed where appropriate. Changes in symptom scores and nasal congestion from baseline to follow-up visits will be evaluated using a paired t-test or signed rank test. Multilevel linear mixed models will be built to examine the association between treatment and outcomes. We chose this method because it handles unbalanced data and produces less biased significance than other analysis techniques- due to making use of all available data and incorporating the correlation between time points. Because there are only two time points, an unstructured correlation structure is used. The design effects include main effects of treatment group, time and the group by time interaction, while controlling for study subjects' demographic and clinical factors. We will also examine the different effect between allergic vs non-allergic rhinitis by including it as a covariate and its interaction with treatment in the models. All the analyses use a two-sided test and p<0.05 is considered to be statistically significant.

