1.2 Study Design

This is a multi-center, randomized, double blind study of approximately 50 subjects suffering from moderate to severe nasal congestion. Three sites will participate in enrollment. Those who meet the inclusion/exclusion criteria will be invited to participate in the study.

After signing an Informed Consent Form and providing Demographic Information, Medical History, Allergy History, and Medications, the subject will receive the Sonu Device (device and smartphone [if needed] and the app). Subjects will complete the Total Nasal Symptom Score (TNSS) questionnaire, Visual Analog Scale (VAS) for Headache or Facial Pain, SNOT-22 and PROMIS Sleep Disturbance Questionnaire within the App.

Subjects will be randomized to either receive treatment for two weeks, or sham therapy for two weeks. Interventional treatment arm consists of using Sonu Acoustic Resonance Therapy (ART) for 15 minutes, twice a day. Sham consists of using non-resonant acoustic energy (2 kHz, 2 seconds duration tone every 10 seconds at 50% of therapeutic volume) for 15 minutes, twice a day.

Treatment (or sham) will be completed twice daily, during a morning window from 5am to 12pm and during an evening window from 5pm to 12am. Treatments will automatically stop at 15 minutes. Subjects will complete the TNSS questionnaire and the VAS-HA/FP immediately after the second treatment each day. After the second treatment on the 7th and 14th days subjects will also complete the SNOT-22 and PROMIS questionnaire.

The Total Nasal Symptom Score (TNSS; possible score of 0-12) is a validated patient-reported outcome measure for nasal quality of life research. The TNSS is the sum of 4 symptom subdomains for rhinorrhea, nasal congestion, nasal itching, and sneezing, each self-rated by the subject using a scale of 0=None, 1=Mild, 2=Moderate, or 3=Severe. Subjects will complete the TNSS reflecting on the previous 24 hours at baseline and after the second treatment (treatment or sham), every day over the 2 week period.

The Visual Analog Scale for Headache and/or Facial Pain (VAS-HA/FP) is a measure comprised of a line where patients mark the severity of any headache or facial pain they experience, measured in a range from 0 - 100. Subjects will complete the VAS-HA/FP at baseline and after the second treatment (treatment or sham), every day over the 2 week period.

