1.2 Study Endpoints

Safety and efficacy were evaluated by the following endpoints. Primary Endpoints.

- Primary Safety as defined as a lack of serious adverse events (SAEs).
- Primary effectiveness as defined by a statistically significant improvement in nasal congestion sub-score of TNSS, comparing baseline congestion at screening versus daily congestion averaged over 2 weeks (Sonu vs. Sham).

Secondary Endpoints

- Secondary Safety as defined as a lack of adverse events (AEs).
- Secondary effectiveness as defined by a statistically significant improvement in 24hour reflective TNSS comparing baseline TNSS at screening versus daily TNSS averaged over 2 weeks (Sonu vs. Sham).

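### The primary Sonu-versus-sham test is not tied to the 2-week average, and adjusting it for baseline congestion would gain power at no cost in data

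*Combined protocol and SAP*

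**What the plan says.** Section 1.2 Study Endpoints sets the primary criterion: "Primary effectiveness as defined by a statistically significant improvement in nasal congestion sub-score of TNSS", with the comparison given as "comparing baseline congestion at screening versus daily congestion averaged over 2 weeks (Sonu vs. Sham". Variable, baseline, follow-up summary and contrast are therefore all stated there.

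Section 1.2 Study Design describes the data: "Subjects will complete the TNSS reflecting on the previous 24 hours at baseline and after the second treatment (treatment or sham), every day", for two weeks.

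Section 2, Statistical Plan, lists two analyses that could bear on this endpoint.

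- A within-subject test: "Changes in symptom scores and nasal congestion from baseline to follow-up visits will be evaluated using a paired t-test or signed rank test". It does not say whether this is done per arm or pooled.
- Mixed models relating treatment to outcomes. On the time structure: "Because there are only two time points, an unstructured correlation structure is used". On the terms: "The design effects include main effects of treatment group, time and the group by time interaction", with control for demographic and clinical factors. Rhinitis type and its interaction with treatment are also to be examined.

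On significance: "All the analyses use a two-sided test and p<0.05 is considered to be statistically significant". Section 2 does not use the word primary and does not mention the 2-week average.

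**The concern.** There are two layers.

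The first is one of linkage. Section 2 does not say which of its analyses decides primary effectiveness. The paired test names congestion but compares subjects only with themselves. The mixed model compares arms but names no outcome and no deciding term. The choice of term matters: with baseline as the reference time, the group main effect is the baseline difference between arms, and only group-by-time compares change between arms. The two time points are not identified either, although the congestion score is collected at baseline and daily.

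The second is one of method. Read in the way that fits the endpoint, the model has one baseline value and one 2-week average per subject, an unstructured covariance, and free means for each arm at each time. With complete data its group-by-time term is the between-arm difference in mean change. That is valid, but it uses the baseline score less efficiently than adjustment does. With about 50 subjects, the loss may be worth recovering.

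**Working it through.** **No figure to reproduce.** The documents give a total of about 50 subjects. They give no SD, effect size, power or allocation ratio.

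**Inputs (assumed unless stated).**

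- 25 per arm: the stated total of about 50, split 1:1 by assumption.
- Baseline SD s_b = 0.5. On the 0-to-3 item this is the SD if scores divide evenly between 2 (moderate) and 3 (severe).
- SD of the 2-week average s_f = 0.6 or 0.7.
- Correlation r between baseline and the 2-week average = 0.3 or 0.5.
- True difference 0.5, with 0.3 as a sensitivity case.
- Two-sided 0.05, from section 2.

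**Formulas.**

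- Group-by-time (change score): variance s_b² + s_f² − 2·r·s_b·s_f, with 48 df.
- Baseline-adjusted: residual variance s_f²·(1 − r²), with 47 df.
- The first variance minus the second is (s_b − r·s_f)², which is never negative. Adjustment therefore cannot have the larger residual variance; its price is one degree of freedom.
- Power from the noncentral t, with noncentrality = difference / (SD × √(2/25)), where √(2/25) = 0.283.

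**One case in full: s_f = 0.6, r = 0.3.**

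- Change: 0.25 + 0.36 − 0.18 = 0.43, SD 0.656; noncentrality 0.5/(0.656 × 0.283) = 2.70; power 0.752.
- Adjusted: 0.36 × 0.91 = 0.3276, SD 0.572; noncentrality 0.5/(0.572 × 0.283) = 3.09; power 0.857.
- Check: 0.43 − 0.3276 = 0.1024 = (0.5 − 0.18)².

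**All cases, true difference 0.5** (gains taken from unrounded power):

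| s_f, r | SD of change | Residual SD | Group-by-time | Adjusted | Gain |
|---|---|---|---|---|---|
| 0.6, 0.3 | 0.656 | 0.572 | 0.752 | 0.857 | 0.104 |
| 0.6, 0.5 | 0.557 | 0.520 | 0.875 | 0.915 | 0.040 |
| 0.7, 0.3 | 0.728 | 0.668 | 0.663 | 0.737 | 0.074 |
| 0.7, 0.5 | 0.624 | 0.606 | 0.792 | 0.815 | 0.023 |

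**True difference 0.3, same order.** Group-by-time 0.354, 0.463, 0.298, 0.384; adjusted 0.442, 0.516, 0.343, 0.403. The ranges are 30% to 46% and 34% to 52%.

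**Limits.** The calculation treats the average as roughly normal, leaves out the other covariates (the plan does not list them) and ignores the small loss from chance baseline imbalance, so the smallest gains are slightly overstated.

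**The case against.** This is one short document, and its parts can be read together. The endpoint section fixes the variable, the baseline, the 2-week average and the contrast. That endpoint has exactly two values per subject, which matches the two time points in the model, and only group-by-time compares change between arms. The inference is short. It stands, and it reduces the linkage problem to a missing cross-reference.

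Three stronger readings are tempting, and the documents do not support them.

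- *No sham comparison is planned.* Section 2 relates treatment to outcomes through the mixed model and prefers that model: "We chose this method because it handles unbalanced data and produces less biased significance than other analysis techniques".
- *The paired test could carry the efficacy claim.* The plan does not propose this, and the endpoint's Sonu-versus-sham wording rules it out. False-positive rates for such a use would describe a misuse that the plan does not contain.
- *The second time point is a single day, such as day 14.* The endpoint section specifies the 2-week average, section 2 favours the model for using all available data, and no text proposes a single day for this score. A power loss from that choice would be hypothetical.

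Two further objections have force. Every input to the power figures except the total sample size and the test level is assumed, and the absolute levels fall steeply at a difference of 0.3. The gain from adjustment is also modest in some scenarios. Neither reverses the direction of the variance comparison.

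**Conclusion.** The point holds as an improvement worth making. It does not show that the plan lacks a valid primary test: group-by-time, with baseline and the 2-week average as the two time points, would test the stated endpoint. What is missing is the statement that this term is primary and that the second time point is that average, together with a label for the paired tests.

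The main gain is in method. Baseline adjustment raises power by about 2 to 10 percentage points at a true difference of 0.5, and by about 2 to 9 points at 0.3. These sizes rest on the assumed SDs, correlations, 1:1 split and differences. The direction rests only on the variance identity, apart from the small costs noted with the calculation; when r·s_f is close to s_b the gain all but vanishes.

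**What to change.** Amend both the paired-test sentence and the mixed-model sentences of section 2, so that two competing primary analyses do not remain. Suggested text:

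> The primary test is the Sonu-versus-sham difference in 2-week average daily congestion, adjusted for baseline congestion, at two-sided 0.05. The mixed models and the rhinitis-type interaction are supportive. Within-arm changes are descriptive and support no efficacy claim.

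If the sponsor prefers to keep the mixed model as primary, section 2 should name the group-by-time term, give baseline and the 2-week average as the two time points, and leave the rhinitis-type interaction out of the primary model. With that interaction included, the meaning of the treatment terms depends on coding. Either choice should be fixed before unblinding.

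The cost is wording only, with no added subjects, questionnaires or procedures. There are two small downsides. Within-arm p-values are given up. A subject with no post-baseline score also adds nothing to the adjusted comparison.

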The SNOT-22 is a validated patient-reported outcome measure for quality-of-life research, comprised of 22 questions with possible answers ranging from 0 - 5. The SNOT-22 will be collected at baseline, after week 1 of therapy or sham, and after week 2 of therapy or sham. All results will be recorded via the App.

The PROMIS Sleep Disturbance Scale is a measure that assesses the pure domain of sleep disturbance in adults 18 years and older. It consists of 8 questions with possible

answers ranging from 1 - 5. This scale will be completed at baseline, after week 1 of therapy or sham, and after week 2 of therapy or sham. All results will be recorded via the App.

At the end of the two weeks participants will be asked one question regarding their thought about which arm of the study they were randomized to.

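### Cheap improvement: the effectiveness analysis reduces up to 14 daily scores to one mean per subject and treats baseline as an outcome; a baseline-adjusted daily model would use the same data better

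*Combined protocol and SAP*

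**What the plan says.** Section 1.2 Study Design sets the collection schedule: "Subjects will complete the TNSS questionnaire and the VAS-HA/FP immediately after the second treatment each day". Over two weeks this gives up to 14 post-baseline scores per subject.

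Section 1.2 Study Endpoints reduces them to one number. Primary effectiveness (congestion item, 0-3) is defined by "comparing baseline congestion at screening versus daily congestion averaged over 2 weeks (Sonu vs. Sham"; secondary effectiveness (total TNSS) by "comparing baseline TNSS at screening versus daily TNSS averaged over 2 weeks (Sonu vs. Sham".

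Section 2 chooses a multilevel linear mixed model, "due to making use of all available data and incorporating the correlation between time points". It then states: "Because there are only two time points, an unstructured correlation structure is used". On the terms: "The design effects include main effects of treatment group, time and the group by time interaction", with adjustment for demographic and clinical factors that are not named. The two time points are not named either. No section says how the average is formed from an incomplete diary.

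**The concern.** Taken together, the three sections most naturally mean that the model sees two rows per subject: baseline and the 2-week mean. Two things follow.

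- The mixed model can keep a subject who lacks one whole row, but it works on the mean and not on the days behind it. A mean of 5 recorded days enters exactly as a mean of 14 does. The subject's earlier course, and that of the other subjects, cannot inform the unrecorded days.
- With baseline as an outcome row and a free group effect, the group-by-time term is the arm difference in change from baseline (both rows present, before covariates). That carries the full noise of a single baseline score.

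At stake are a modest bias if diaries stop unequally between arms while scores are still changing, some attenuation if the effect builds over time, and a larger and more certain loss of precision.

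**Working it through.** **Inputs from the documents.** 14 daily scores plus baseline; congestion item 0-3; about 50 subjects; two-sided 0.05. The sample size has no calculation behind it, so there is no plan figure to reproduce.

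**Assumed, for illustration only.** 25 per arm; between-subject and within-subject SD 0.5 each; 0.8-point change; stoppers leave after day 5; recorded days are averaged.

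**1. Structure.** Up to 15 records become 2 rows. An unstructured matrix has k(k+1)/2 parameters: 3 for k = 2, but 14×15/2 = 105 for 14 days. The present structure therefore cannot simply be carried over to daily data with about 50 subjects.

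**2. Weight of a short diary.** In a change score the subject effect cancels, so the variance is 0.25 + 0.25/m for m recorded days: 0.268 at m = 14 and 0.300 at m = 5, a ratio of 1.12. Equal weighting costs little precision in itself; what matters is a time trend combined with stopping.

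**3. False advantage, no device effect, random stopping on sham only.** It equals the stopping fraction times (14-day mean change minus 5-day mean change).
- *Linear course.* 0.8×7.5/14 = 0.429 and 0.8×3/14 = 0.171, a gap of 0.257.
- *Change reached by day 3, then flat.* (0.8/3 + 1.6/3 + 12×0.8)/14 = 0.743 and (0.8/3 + 1.6/3 + 3×0.8)/5 = 0.640, a gap of 0.103.

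| Sham stopping | Linear: points | Linear: type I error (simulated) | Day-3 plateau: points | Day-3 plateau: type I error (simulated) |
|---|---|---|---|---|
| 10% | 0.026 | 5.3% | 0.010 | 5.1% |
| 20% | 0.051 | 6.4% | 0.021 | 5.2% |
| 30% | 0.077 | 8.0% | 0.031 | 5.5% |

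Equal 20% stopping in both arms gives 0.00 and 5.0%.

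**4. Attenuation.** If the effect builds linearly to 0.8, the true 14-day difference is -0.429. With 20% stopping per arm it becomes -(0.8×0.429 + 0.2×0.171) = -0.377.

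**5. Baseline adjustment.** The 14-day mean has variance 0.25 + 0.25/14 = 0.268, a baseline score 0.50, and their covariance is 0.25. Adjusting for baseline leaves 0.268 - 0.25²/0.50 = 0.143, against 0.268 for the change score. Standard errors of the arm difference are √(2×0.268/25) = 0.146 and √(2×0.143/25) = 0.107, so 0.429 is 2.93 or 4.01 standard errors. Power is about 81-82% for the change score and 97% adjusted. With 20% stopping per arm, power is about 69% and 91%.

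Adjustment does not remove the bias in step 3. Because the standard error is smaller, type I error in the 30% linear case rises from 8.0% to 10.5%.

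**6. What a daily model adds.** A daily model with random intercept and AR(1) was simulated. In the 30% linear case the estimate was +0.002 with type I error 4.3%. In the 20%-per-arm case of step 4 power was 96%, against about 90% for the baseline-adjusted mean.

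That covariance matched the simulated data. A further case let about 30% of sham subjects stop, more often those with worse early scores, and let individual slopes vary with an SD of 0.8 or 1.2 points by day 14. The daily model was then off by about +0.03 and +0.05, and the available-day mean by -0.07 and -0.06 (Sonu minus sham; negative favours Sonu).

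**The case against.** The strongest reply is that nothing here is wrong. Two time points is a correct description of an endpoint that compares baseline with a 2-week mean. A missed diary day is not available data, and averaging the recorded days uses every recorded score. A reader might infer that section 2 contradicts the daily schedule, or that its claim to use all available data is false; the documents support neither reading.

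The bias also rests on assumptions. It needs a slow course together with unequal or response-related stopping, and it nearly vanishes with an early plateau. Most of the power gain comes from baseline adjustment, which needs no daily model. And a daily model with a badly chosen covariance carries bias of its own.

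All of this stands, and it sets the size of the point. What it does not answer is that the two-row model cannot draw on the time course for unrecorded days, and that a change-score contrast is less precise than a baseline-adjusted one. Both can be improved with data already being collected.

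**Conclusion.** A worthwhile, inexpensive improvement; not an error in the plan. On the natural reading, the primary and secondary effectiveness analyses rest on two rows per subject. Under the stated assumptions the possible false advantage is 0.01 to 0.08 points on a 0-3 item at 10-30% sham-only stopping, with type I error about 5-8%; the upper end needs about 30% of one arm to stop early while scores are still falling. An effect building to 0.8 would shrink from -0.43 to -0.38 with 20% stopping per arm. The firmer gain is precision: power of about 97% rather than 81% with complete diaries, from baseline adjustment alone, if the assumed SDs are near the truth.

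A reader might infer that the trial's type I error is inflated. The documents do not support that: they give no dropout rate, SD or time course, and equal stopping produces no bias under the null. Nor does the daily model guarantee an unbiased result; it assumes missing at random and an adequate covariance.

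**What to change.** In section 2, replace the sentence on two time points and the one on design effects, for congestion and total TNSS, with a plan along these lines:

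- Model the scores for days 1-14 with baseline score as a covariate and fixed effects for arm, day (categorical), arm-by-day and named demographic and clinical covariates.
- Report the arm difference averaged equally over days 1-14 as the primary estimate. This leaves the endpoint unchanged.
- Prespecify a structured covariance that lets subjects differ in time course, for example random intercept and slope, with small-sample inference.
- State that the model assumes missing at random, and add one delta-adjusted sensitivity analysis. For scale, stopping after day 5 by 10%, 20% or 30% of an arm loses 9/14 of those subjects' days, or 6.4%, 12.9% or 19.3% of the arm's days. A delta of one point would then move the congestion estimate by 0.064, 0.129 or 0.193.

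If the sponsor prefers the per-subject mean, analyse it with baseline as a covariate, state that recorded days are averaged, and add the same sensitivity analysis. This secures most of the precision but not the protection against unequal stopping.

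**Cost.** SAP wording and modest programming; no new data and no change to the sample size. Downsides: the covariance must be fixed in advance and a poor choice can leave bias (about 0.03 to 0.05 points in the varying-slope case above); missing at random is still assumed; and subjects with a baseline but no diary score no longer contribute to the primary estimate.

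### The two-time-point mixed model, as most plausibly read, tests a raw change score that the covariates barely reach; modelling the 2-week mean with baseline as a covariate is near-free precision of uncertain size.

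*Combined protocol and SAP*

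**What the plan says.** The primary effectiveness endpoint (section 1.2, Study Endpoints) is improvement in the congestion sub-score, "comparing baseline congestion at screening versus daily congestion averaged over 2 weeks (Sonu vs. Sham"). The secondary endpoint treats TNSS in the same way. Each endpoint therefore has two quantities per subject: a baseline value and the mean of the daily scores over two weeks.

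Section 2 plans multilevel linear mixed models. On the covariance it says "Because there are only two time points, an unstructured correlation structure is used". On the fixed effects it says "The design effects include main effects of treatment group, time and the group by time interaction", "while controlling for study subjects' demographic and clinical factors". Rhinitis type (allergic or non-allergic) is to be examined by "including it as a covariate and its interaction with treatment in the models".

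The section does not say which two time points are meant, which coefficient is the primary test, or which demographic and clinical factors are included. It does not name the baseline score as a covariate, constrain the arms to a common baseline mean, or cross any covariate with time.

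**The concern.** If baseline is one of the two outcome rows and group-by-time is the test, three things follow.

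- Baseline is removed by subtraction, with its slope set to 1 and not estimated. When the true slope is below 1, this adds noise and over-corrects any chance baseline difference between arms.
- Covariates entered only as main effects shift both rows of a subject equally, so they cancel from the change. The stated covariate control then contributes almost nothing to the Sonu-versus-sham contrast.
- Rhinitis type by treatment, without time, describes a difference in level pooled over baseline and follow-up. The question asked is whether the treatment effect differs by rhinitis type.

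The trial is small, a "randomized, double blind study of approximately 50 subjects suffering from moderate to severe nasal congestion", so avoidable variance matters.

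**Working it through.** **Inputs.** From the documents: about 50 subjects, a congestion item scored 0 to 3, and two-sided 0.05. The plan gives no SD, correlation, effect size or power, so there is no planned figure to reproduce. Assumed:

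- Baseline SD (SDb) 0.3 to 0.5. If entry at moderate to severe means a rating of 2 or 3, a 90/10 split gives √(0.9 × 0.1) = 0.3 and a 50/50 split gives 0.5.
- SD of the 2-week mean (SDf) 0.5 to 0.7.
- Correlation r between them 0.2 to 0.5.
- 1:1 allocation, 25 per arm.

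**Step 1: what group-by-time estimates.** Let B be baseline, F the 2-week mean and D = F − B. In the two-row model the mean of D contains only time and group-by-time; arm main effects and time-constant covariates cancel. Given D, the model for B has its own free intercept, arm effect, covariate effects and slope on D. With complete data, B therefore carries no information about group-by-time, which is estimated from D alone as the difference in mean change.

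REML fits to simulated 50-subject trials confirm this. Over 40 complete-data trials, adding age, sex and rhinitis type changed the estimate by less than 1e-14 and its SE by less than 2e-7. In one separate data set the estimate was −0.34991 (SE 0.14974) with covariates, without them, and as the raw change difference.

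Missing follow-up breaks the separation only slightly. With 5 of 50 follow-ups missing at random (300 trials), the covariates moved the estimate by a median of 0.003 and at most 0.027, against a mean SE of 0.186.

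**Step 2: variance of the two analyses.**

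Variance ratio (baseline-adjusted / change score) = SDf²(1 − r²) / (SDb² + SDf² − 2·r·SDb·SDf)

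Over the assumed ranges this runs from 0.60 to 1.00. The lower end is SDb = SDf = 0.5, r = 0.2: 0.24/0.40. The upper end is reached when the true slope r·SDf/SDb equals 1, for example SDb 0.3, SDf 0.6, r 0.5: 0.27/0.27.

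| SDb | Range over SDf and r | Ratio at SDf 0.6, r 0.3 | 50 × ratio |
|---|---|---|---|
| 0.5 | 0.60–0.94 | 0.3276/0.430 = 0.76 | 38 |
| 0.4 | 0.73–0.99 | 0.3276/0.376 = 0.87 | 44 |
| 0.3 | 0.86–1.00 | 0.3276/0.342 = 0.96 | 48 |

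Estimating the slope costs a factor (n − 3)/(n − 4) = 47/46 = 1.022. If the change-score analysis had 80% power, adjusted power would be Φ((1.96 + 0.84)/√(1.022 × ratio) − 1.96), or about 89%, 84% and 81% for the three rows. With a true slope of 1, simulated power was about 79% against 80%.

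**Step 3: chance imbalance.** If the arms differ by d at baseline, the expected change contrast shifts by (1 − slope)·d in size. At SDb 0.4, SDf 0.6, r 0.3 the slope is 0.3 × 0.6/0.4 = 0.45. The SE of d is 0.4 × √(2/25) = 0.113, so a one-SE imbalance shifts the contrast by 0.55 × 0.113 = 0.06. The change-score SE is √0.376 × √(2/25) = 0.17.

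**Step 4: rhinitis type.** Without time, the arm-by-type term is a weighted average of the baseline and follow-up differences. The weight on follow-up is (SDb² − c)/(SDb² + SDf² − 2c), with c = r·SDb·SDf. At the Step 3 values, c = 0.072 and the weight is 0.088/0.376 = 0.23. A true difference in effect of −0.6 at follow-up, with none expected at baseline, appears as −0.6 × 0.23 = −0.14. In 300 simulated trials the term averaged −0.13 and was rejected in 12%. Arm by type in the baseline-adjusted post-baseline model averaged −0.59 and was rejected in 42%. Over the assumed ranges the weight never exceeds 0.50.

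**The case against.** The strongest reply is that the criticised model is inferred. Baseline severity could be among the clinical factors, and SNOT-22 and PROMIS each have exactly two post-baseline assessments, so the two time points might be those. That reading does not suit congestion or TNSS, whose endpoints pair baseline with a single average. The inference still has to be stated as one, and the certain gap is that the time points and the primary term are unnamed.

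The gain may also be negligible. Over the assumed ranges the median ratio is about 0.90, about 48% of grid points exceed 0.90, and a correlation above 0.5 would shrink the gain further. Grid medians are not probabilities, but this stands: a large gain cannot be promised, and a loss of about 2% is possible.

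The small effect of covariates under missing data depends on mild assumptions. With stronger covariate effects and about 20% missingness depending on arm and covariates, two stress simulations gave median shifts of 0.026 and 0.04 and maxima of 0.12 and 0.10, against an SE of about 0.19 to 0.20. The shift is modest, but not nil.

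Finally, rhinitis type by treatment may be shorthand for an interaction with the treatment effect. If so, only the wording needs correcting. The question is not a listed endpoint, and the −0.6 used above is illustrative.

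**Conclusion.** The concern holds, with moderate confidence, as an efficiency point. The planned contrast is unbiased under randomization and its type I error is sound. On the reading that best fits the endpoint, the primary test is an unadjusted change score, and the promised covariate control barely touches it. The gain from estimating the baseline slope runs from a variance reduction of about 40% to nothing, with a loss of about 2% at worst. Its size rests on assumed SDs and correlation and cannot be fixed from the documents. The rhinitis-type term, taken as worded, recovers at most half of the difference it is meant to measure under the same assumptions.

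**What to change.** 1. Name the two time points and the coefficient that is the primary test.
2. Make the primary analysis a model of the 2-week mean congestion score on treatment arm, baseline congestion and a prespecified covariate list including rhinitis type. The arm coefficient is the test.
3. Alternatively, keep baseline as an outcome row, constrain its mean to be equal across arms, and cross the covariates with time.
4. Test the rhinitis-type difference with arm by rhinitis type in the post-baseline model, or arm by time by rhinitis type in the two-row model.
5. Use the same model for TNSS, with baseline TNSS.

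The cost is SAP wording, no new data, and a few degrees of freedom. A subject with no daily score drops out of the post-baseline model. The constrained two-row version keeps that subject, which fits the plan's aim of using all available data.
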